- E. Can donor-subjects withdraw their materials at any time, and/or withdraw the identifiers that connect them to their materials?
 - i. How will requests to withdraw materials be handled (e.g., material no longer identified: that is, anonymized) or material destroyed)?
- **F.** Describe the provisions for protection of participant privacy
- **G.** Describe the methods for the security of storage and sharing of materials

6. **Statistical Considerations:** Describe the statistical analyses that support the study design.

Sample size calculations were performed using PASS 2002 (Hintze J. 2001. NCSS and PASS Number Cruncher Statistical Systems. Kaysville, Utah.). In our preliminary magnetic resonance spectroscopy experiments (see preliminary studies), under hypoglycemic conditions, we observed significantly greater fractions of glial oxidative metabolism supplied by acetate in T1DM subjects compared to non-diabetic controls $(0.19 \pm 0.066 \text{ vs } 0.10 \pm 0.020; \text{ a } 90\% \text{ increase in diabetics compared to controls})$. We will expect differences between severe hypoglycemia unaware and control subjects in this study to be on a similar scale. With a pooled standard deviation of 0.033, our proposed sample sizes (17 diabetic subjects and 17 non-diabetic controls) will provide 80% power at the two-sided 0.05 significance level to detect differences of 0.033 between diabetic subjects and non-diabetic controls representing a 33% increase from non-diabetic subjects. In short, we should easily have sufficient numbers of to address our primary endpoint of enhanced ketone body uptake and metabolism following recurrent hypoglycemia. Using this data, our proposed sample sizes of 17 subjects per group will provide >80% power to detect a 20% difference in the severe hypoglycemia unaware compared to each control group. We anticipate the changes seen will be much greater than that. Because small effects cannot be detected with sufficient power, conclusions based on failure to reject the null hypothesis will be avoided.

The same group size considerations apply to the cohorts studied with glucose/lactate coinfusions and the cognitive performance analysis under ketone infusion outside of the MRI scanners.

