Data analysis will be performed using SAS statistical software version 8.2. Prior to the fundamental analysis, all data will be appropriately screened for accuracy, missing data, outliers and agreement with assumptions for the analyses. Univariate descriptive statistics and plots will first be employed to determine out-of-range values as well as plausible means and standard deviations. Non-normal variables will be identified through the inspection of normal probability plots and with the Kolmogorov-Smirnov test. If required, appropriate transformations or non-parametric tests will be applied to variables in violation of the model assumptions. [name]., the GCRC biostatistician, is available for advice in data analysis.

To test the hypothesis that patients with hypoglycemia unawareness exhibit enhanced CNS ketone body metabolism we will assess brain beta-hydroxybutyrate transport and its absolute levels and the ratio of brain beta-hydroxybutyrate contribution to the neuronal and astroglial TCA cycle. In addition, we will determine the absolute concentration of brain neurotransmitter levels using proton NMR. Group comparisons will be assessed by analysis of variance (ANOVA) for repeated measures. Data will be tested for multisample sphericity using Mauchly's and Box tests. If the assumption of homogenous covariance matrices is violated a covariance pattern model will be employed to allow for separate sets of covariance parameters for type 1 diabetic vs. nondiabetic controls. Evaluation of a significant diagnosis by clamp condition interaction will be determined by paired or unpaired t-tests (for within and between subjects factors respectively), using the interaction variance term from the ANOVA with a Holm correction for multiple testing.

involvement.		
Children		Fetal material, placenta, or dead fetus
☐ Non-English Speaking	Prisoners	☐ Economically disadvantaged persons
Decisionally Impaired	Employees	Pregnant women and/or fetuses
☐ Yale Students		earing potential
		en who are wards of the state as potential subjects? Yes
No (If yes, see Instructions	section VII #4 for further	requirements)

7. Subject classification: Check off all classifications of subjects that will be targeted for enrollment in the

8. Inclusion/Exclusion Criteria: What are the criteria used to determine subject inclusion or exclusion?

Inclusion criteria for subjects:

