12. **Statistical Considerations:** Describe the statistical analyses that support the study design.

Sample size calculations were performed using PASS 2002 (Hintze J. 2001. NCSS and PASS Number Cruncher Statistical Systems. Kaysville, Utah.). In our preliminary magnetic resonance spectroscopy experiments (see preliminary studies), under hypoglycemic conditions, we observed significantly greater fractions of glial oxidative metabolism supplied by acetate in T1DM subjects compared to nondiabetic controls (0.19 \pm 0.066 vs 0.10 \pm 0.020; a 90% increase in diabetics compared to controls). We will expect differences between severe hypoglycemia unaware and control subjects in this study to be on a similar scale. With a pooled standard deviation of 0.033, our proposed sample sizes (17 diabetic subjects and 17 nondiabetic controls) will provide 80% power at the two-sided 0.05 significance level to detect differences of 0.033 between diabetic subjects and nondiabetic controls representing a 33% increase from nondiabetic subjects. In short, we should easily have sufficient numbers of to address our primary endpoint of enhanced ketone body uptake and metabolism following recurrent hypoglycemia. Using this data. our proposed sample sizes of 17 subjects per group will provide >80% power to detect a 20% difference in the severe hypoglycemia unaware compared to each control group. We anticipate the changes seen will be much greater than that. Because small effects cannot be detected with sufficient power, conclusions based on failure to reject the null hypothesis will be avoided.

Data analysis will be performed using SAS statistical software version 8.2. Prior to the fundamental analysis, all data will be appropriately screened for accuracy, missing data, outliers and agreement with assumptions for the analyses. Univariate descriptive statistics and plots will first be employed to determine out-of-range values as well as plausible means and standard deviations. Non-normal variables will be identified through the inspection of normal probability plots and with the Kolmogorov-Smirnov test. If required, appropriate transformations or non-parametric tests will be applied to variables in violation of the model assumptions. [name]., the GCRC biostatistician, is available for advice in data analysis.

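### Follow-up t-tests are tied to one pooled ANOVA error while separate group variances hang on a pre-test, so within-group error rates can move well away from 5%

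*Combined protocol and SAP*

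**What the plan says.** The analysis text is in Section V, item 6 (Statistical Considerations), and is repeated almost unchanged as item 12 of the same section.

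- Main model: "Group comparisons will be assessed by analysis of variance (ANOVA) for repeated measures".
- Pre-test: "Data will be tested for multisample sphericity using Mauchly's and Box tests". No significance level is given for either test.
- Fallback: "If the assumption of homogenous covariance matrices is violated a covariance pattern model will be employed", with separate parameters for T1DM and controls.
- Follow-up: a significant diagnosis-by-clamp interaction is broken down by paired tests within a group and unpaired tests between groups, "using the interaction variance term from the ANOVA with a Holm correction for multiple testing".

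Neither item says which variance the follow-up tests use when the fallback model has replaced the ANOVA.

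The sample-size paragraph of item 6 reports pilot values under hypoglycemia of 0.19 ± 0.066 in T1DM and 0.10 ± 0.020 in controls. It gives no pilot sample size and does not say whether ± is an SD or a standard error. It plans 17 subjects per group.

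**The concern.** The plan's own pilot points to a far more variable T1DM group. With equal group sizes, the ANOVA interaction error is the average of the two groups' change variances. That average is too small for the more variable group and too large for the other. A paired euglycemia-versus-hypoglycemia test on it therefore rejects too easily in T1DM and too rarely in controls. These are the tests that will be used to say which group responds to hypoglycemia, so the error falls on the interpretation of the interaction.

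Making group-specific variances depend on a pre-test adds a second weakness. At 17 per group such a test often misses moderate heterogeneity.

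**Working it through.** **The plan's own figure.** The plan states that 17 per group "will provide 80% power at the two-sided 0.05 significance level to detect differences of 0.033 between diabetic subjects and non-diabetic controls". With SD 0.033, a noncentral t calculation on 32 df gives 80.7%, so the stated power reproduces. The plan states no false-positive rate for the follow-up tests, so there is none to reproduce.

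**Inputs.**
- 17 per group and two-sided 5% (item 6).
- Pilot SD ratio 0.066/0.020 = 3.3, so the variance ratio is 3.3² = 10.89. If ± means standard error, the SD ratio is still 3.3 provided the pilot groups were of equal size.
- SD of the within-subject change by group: not given. Assumption: SD ratio 3.3, with 2 and 1.5 as alternatives.
- Holm family: not specified. Assumption: the two within-group tests.

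**Within-group test on the pooled term.** With s²p = (s²₁ + s²₂)/2 on 32 df and change-variance ratio v (T1DM over control), the T1DM statistic is inflated by about √(2v/(v+1)).
- v = 10.89: √(21.78/11.89) = 1.353; 1.96/1.353 = 1.448; two-sided tail 14.8%.
- v = 4 (SD ratio 2): √1.6 = 1.265; 1.96/1.265 = 1.549; tail 12.1%.
- v = 2.25 (SD ratio 1.5): √1.385 = 1.177; 1.96/1.177 = 1.666; tail 9.6%.

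Simulation (200,000 trials, normal data, no true change in T1DM) agrees. The pre-test here is a 5% F-test on the change variances, standing in for the plan's tests.

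| SD ratio | Within-T1DM, pooled term | Within-T1DM, own variance | Pre-test misses | Within-T1DM if tests switch with pre-test |
|---|---|---|---|---|
| 3.3 | 14.8% | 5.0% | 0.5% | about 5% |
| 2 | 12% | 5.0% | 23% | about 6.5% |
| 1.5 | 9.4% | 5.0% | 66% | about 7.5% |

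Box's test itself at 0.05 rejects in over 99.9% of trials at SD ratio 3.3.

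**Controls at ratio 3.3.** The statistic is shrunk by √(2/11.89) = 0.410, and the false-positive rate is about 0.01%. For a true change of 1 control SD, the own-variance statistic centers near √17 = 4.12 against a critical value of 2.12 (16 df), giving 97% power. On the pooled term it centers near 4.12 × 0.410 = 1.69 against 2.04 (32 df), giving 27%.

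**Interaction gate plus Holm, pooled term, ratio 3.3, no change in T1DM.**

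| True change in controls | Within-T1DM false positives |
|---|---|
| none | 5.1% (2.4% with own variances) |
| 2 SD | 7.5% |
| 3 SD | 11% |
| 4 SD | 14.4% |
| 5 SD | 15% |

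**Sensitivity to the carried-over ratio.** Suppose only the hypoglycemia SD differs between groups, and the euglycemia SD equals the control value in both. With within-subject correlation r, the change-variance ratio is (1 + 10.89 − 6.6r)/(2 − 2r). This is 5.9 at r = 0 and 16.5 at r = 0.8, and the pooled-term rate is 13.5% to 15.6%.

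**Interaction and between-group tests.** With equal group sizes, a pooled-variance comparison of the two groups runs at 5.6% at ratio 3.3. Whether the interaction variance is the right error for an unpaired comparison at a single clamp condition is a different question and is not examined here.

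**The case against.** The strongest reply is that 15% is not the error rate of the plan as a whole. A reader might infer that within-T1DM tests simply run at 15%. The documents do not support that, for three reasons.

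- The pilot spreads are between-subject values of an acetate measure under hypoglycemia. The tests concern within-subject changes, whose SDs are not given. Without a pilot sample size, no formal test of the pilot variances is possible either.
- At the pilot ratio the pre-test almost always fires. If the follow-up tests then use the fallback model's variances, the rate is about 5%. The pre-test does its harm at moderate ratios, where the pooled-term rate is nearer 9% to 12%.
- Follow-up is gated by the interaction and Holm-corrected, which brings the rate to about 5% when neither group changes.

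A reader might also infer that the asymmetry manufactures the interaction. It does not: the interaction must be significant first, and its test runs at 5.6%. The plan also says it will not draw conclusions from non-significance, which limits the harm of a missed change in controls. Nor do the documents support a claim about unequal losses inflating between-group tests. They give no expected losses, and the fallback would nearly always be in force at the pilot ratio.

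Three things stand. The text names the ANOVA term without exception. The gate and Holm do not protect T1DM when controls truly change and T1DM does not. Even on the generous reading, 6.5% to 7.5% remains at SD ratios 2 to 1.5. Transformation or a non-parametric test, which the plan allows when assumptions fail, is not linked to the choice of follow-up error term.

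**Conclusion.** The point holds in conditional form. The plan leaves its follow-up error term unreconciled with its own fallback model. Read literally, and with change SDs in the pilot ratio, the within-T1DM test can reach about 15% before the gate and Holm. After both it lies between about 5% and 15%, depending on how far controls truly change. The within-control test becomes very conservative, with power for a 1-SD change down from 97% to 27%. Read generously, with the tests switching when the pre-test rejects, the excess is small: none to speak of at the pilot ratio, and 1.5 to 2.5 percentage points at SD ratios 2 to 1.5. These figures rest on normal data, 17 per group, ± read as SD, a Holm family of two, and a change-SD ratio that the documents do not supply. The point should be fixed because the remedy is cheap. It does not undermine the interaction test.

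**What to change.** In items 6 and 12, make the covariance pattern model with separate T1DM and control covariance parameters the analysis from the start, with Satterthwaite or Kenward-Roger degrees of freedom. Remove its dependence on a homogeneity pre-test. State that every follow-up contrast comes from that model, so that each within-group test uses its own group's variance. Keep the interaction gate and Holm, and name the Holm family. For outcomes with only two clamp conditions sphericity holds automatically and Mauchly's test can go. This does not extend to the enrichment time courses or regional comparisons in the Research Plan, where the covariance structure over more than two levels has to be specified.

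The cost is a paragraph of wording, with no change to data collection or sample size, since the model is already named in the plan. If the variances turn out equal, a within-group test has 16 rather than 32 df: a critical value of 2.12 instead of 2.04, or intervals about 4% wider (2.120/2.037 = 1.041).

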- Cohort 1: Subjects from group 1 and group 2 will be scheduled for three study sessions as described below. A screening visit, an MR spectroscopy scan without hyperinsulinemic clamp (euglycemia) and an MR spectroscopy scan during a hyperinsulinemic clamp (hypoglycemia) with a tracer infusion.
- Cohort 2: Subjects from group 1 and group 2 will be scheduled for two study sessions. A screening visit as described below. An MR spectroscopy scan that will be conducted during a hyperinsulinemic clamp (combined eu- and hypoglycemia) together with a tracer infusion.
- Cohort 3: Subjects from group 1 and group 2 will be scheduled for two studysessions. A screening visit as described below. An MR spectroscopy scan conducted during a hyperinsulinemic clamp (combined eu- and hypoglycemia) without a tracerinfusion.
- Cohort 4: Healthy subjects from group 2 will be scheduled for one study session. They will undergo an MR spectroscopy scan without a hyperinsulinemic clamp nor any other i.v. infusions (i.e. no i.v. infusions at all).
- Cohort 5: Subjects from group 1 and group 2 will be scheduled for two studysessions. A screening visit as described below and a hyperinsulinemic clamp together with a non-labeled ketone or saline infusion without an MR spectroscopy scan.

Session A: Screening visit (YNHH Clinical Research Unit):

At the screening visit, study subjects in both the control and T1DM groups will complete the informed consent form for participation in voluntary clinical research. Demographic and clinical data collected will be reviewed by study personnel to confirm eligibility.

Once consented, all subjects will be further screened with a medical history & physical examination, blood work (electrolytes, hematocrit, creatinine, liver function tests and HbA1c) and a 12-lead electrocardiogram (EKG). Detailed subject inclusion and exclusion criteria are listed below (Human subjects – Subject recruitment). Subjects in the T1DM group only will be instructed to record their glucose readings to determine degree and frequency of hypoglycemia as described above. The subject will perform the preliminary cognitive tests at this point if they are selected for Cohort 5 at this point. The two subsequent MR sessions to complete the study will be scheduled at this point. The subject in the control group will have their two MR sessions scheduled without having to record any glucose readings.

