Non-diabetic control subjects will be asked to remain fasting from midnight prior to the study. Upon arrival to the MRRC, their blood glucose will be checked and an IV catheter will be inserted for infusion of insulin and glucose to maintain normal glucose levels and the study will ensue as described below.

For type 1 diabetic subjects receiving insulin via an insulin pump, they will be asked to check their blood glucose at home before bed and on awakening to ensure that the glucose level is above 70mg/dl and below 200mg/dl. They will be instructed to call [name] with any readings outside of this range. Upon arrival to the MRRC, their blood glucose will be checked as a safeguard, and insulin received via the insulin pump will be held. An IV catheter will be inserted for infusion of insulin and glucose to maintain normal glucose levels and the study will ensue as described below.

For type 1 diabetic subjects using multiple injections of insulin per day will be asked to ensure that the glucose level is above 70mg/dl and below 200mg/dl. As a safeguard, they

will be asked to check their blood glucose at home before bed and on awakening. Upon arrival to MRRC, their blood glucose will be checked; a nurse will place intravenous (IV) line to start infusions of glucose and insulin to maintain normal glucose levels.

At 9:00 AM on the day of this NMR session, a standard IV catheter will be inserted and used to deliver a continuous

MRS study design. After a set up period of approximately 30 minutes that includes a 1H MRS scan, subjects will be infused for 120minutes with the isotopic labeled substrate.

insulin infusion (2mU/kg/min) and a variable infusion of 20% dextrose. In addition a second IV line will be placed in the opposite arm to receive a normal saline solution and provide access for obtaining blood samples.

Once subjects arrive in the MR center they will be brought to a hypoglycemic state. The plasma glucose level will be gently lowered to 50 ± 3 mg/dL (see blood draw schedule below).

Once hypoglycemia is achieved tracer will be administered (see Figure above). Depending on the cohort assignment this will involve one of the following infusions:

 a) A 200mmol/l ¹³C /²H- alternate substrate infusion, which will be delivered through a port in the already-established IV site at a rate of 22μM/kg/min.

or

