To test the hypothesis that patients with hypoglycemia unawareness exhibit enhanced CNS alternate fuel metabolism we will assess brain beta-hydroxybutyrate transport and its absolute levels and the ratio of brain alternate fuel contribution to the neuronal and astroglial TCA cycle. In addition, we will determine the absolute concentration of brain

neurotransmitter lebels using proton NMR. Group comparisons will be assessed by analysis of variance (ANOVA) for repeated measures. Data will be tested for multisample sphericity using Mauchly's and Box tests. If the assumption of homogenous covariance matrices is violated a covariance pattern model will be employed to allow for separate sets of covariance parameters for type 1 diabetic vs. nondiabetic controls. Evaluation of a significant diagnosis by clamp condition interaction will be determined by paired or unpaired t-tests (for within and between subjects factors respectively), using the interaction variance term from the ANOVA with a Holm correction for multiple testing.

SECTION VI: RESEARCH INVOLVING DRUGS, BIOLOGICS, RADIOTRACERS, PLACEBOS AND DEVICES

If this section (or one of its parts, A or B) is not applicable, state N/A and delete the rest of the section.

A. DRUGS and BIOLOGICS

1. **Identification of Drug or Biologic:** What is (are) the **name(s)** of the drug(s) or biologic(s) being used? Identify whether FDA approval has been granted and for what indication(s).

[13C] / 2H -labeled BHB

[13C] / 2H -labeled acetate

[13C] / 2H -labeled lactate

[13C] / 2H -labeled glucose

Unlabeled BHB

Unlabeled acetate

Unlabeled lactate

Unlabeled glucose

All protocols which utilize a drug or biologic **not** approved by, but regulated by, the FDA must provide the following information:

- a. What is the Investigational New Drug (IND) **number** assigned by the FDA?
- b. Who holds the IND?

Alternatively, an **exemption from IND filing requirements** may be sought for a clinical investigation of a drug product that is lawfully marketed in the United States. If there is no IND and an exemption is being sought, review the following categories and complete the category that applies (and delete the inapplicable categories):

Exempt Category 1

The clinical investigation of a drug product that is lawfully marketed in the United States can be exempt from IND regulations if all of the following are yes:

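### The follow-up T1DM-versus-control t-tests use the ANOVA interaction error, which omits between-subject variance and makes their standard errors too small

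*Combined protocol and SAP*

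**What the plan says.** Both data-analysis passages (Section V, item 6, and the second Statistical Considerations, item 12) start from a repeated-measures model: "Group comparisons will be assessed by analysis of variance (ANOVA) for repeated measures". Diagnosis is the between-subject factor and clamp condition the within-subject factor. If covariance matrices differ between groups, a covariance pattern model with separate parameters per group takes over.

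The follow-up rule comes next. A significant diagnosis-by-clamp interaction is to be evaluated by "paired or unpaired t-tests (for within and between subjects factors respectively), using the interaction variance term from the ANOVA with a Holm correction". No other error term is given for the unpaired tests. The text does not say what error applies once the covariance pattern model is in use, or which tests make up the Holm family.

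The rule needs outcomes measured in the same person at both glycemic levels. The clearest case is the neurotransmitter outcome ("we will determine the absolute concentration of brain neurotransmitter levels using proton NMR"), with Cohort 3 described in the Research Plan as "An MR spectroscopy scan conducted during a hyperinsulinemic clamp (combined eu- and hypoglycemia") and no tracer.

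**The concern.** An interaction error term is built from each person's change between conditions, so stable differences between people cancel out of it. A comparison of diabetic subjects with controls at one clamp condition is a comparison of different people, and those differences do not cancel. Testing it against the interaction error understates its standard error whenever ρ is positive.

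These follow-up tests decide at which glycemic level the groups are said to differ. If the error is too small, a change confined to hypoglycemia can be reported as also present at euglycemia, which is a different biological conclusion. Holm does not help, because it corrects for the number of tests and takes each p-value as given.

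**Working it through.** **Inputs from the documents.** 17 subjects per group, two-sided α = 0.05, SD 0.033 and difference 0.033 (Statistical Considerations); two clamp levels, euglycemia and hypoglycemia (Research Plan, cohort descriptions).

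**Assumptions.** ρ is not given; 0.3 / 0.5 / 0.7 are used. Equal variances and compound symmetry are assumed unless stated. The interaction variance term is read as the mean square for subject-within-group by clamp condition.

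**The plan's own figure.** With 17 per group the noncentrality is 0.033 / (0.033 × √(2/17)) = √8.5 = 2.92 on 32 df. This gives 80.7% power, agreeing with the stated 80%. That calculation uses the full between-subject SD, so the sample size does not depend on the error term questioned here.

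**Algebra.** Split the variance σ² of one measurement into a subject part ρσ² and a residual part (1−ρ)σ².
- The interaction mean square has expectation σ²(1−ρ).
- A paired within-group contrast has variance 2σ²(1−ρ)/n, so the interaction error is right for it.
- A group difference at one condition has variance 2σ²/n. The planned rule estimates it as 2σ²(1−ρ)/n.
- Planned SE ÷ correct SE = √(1−ρ).

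**Single unpaired test, before gate and Holm.** The critical t on 32 df is 2.037, so the actual type I error is 2·P(t₃₂ > 2.037·√(1−ρ)).

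| ρ | SE factor √(1−ρ) | Actual error of a nominal 5% test |
|---|---|---|
| 0 | 1.00 | 5.0% |
| 0.1 | 0.95 | 6.2% |
| 0.3 | 0.84 | 9.8% |
| 0.5 | 0.71 | 16% |
| 0.7 | 0.55 | 27% |

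**The planned procedure.** Simulation with at least 100,000 datasets per ρ: 17 per group, interaction required at p < 0.05, then Holm. The true group difference is 1 SD at hypoglycemia and zero at euglycemia. Entries are false declarations of a group difference at euglycemia.

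| | ρ = 0.3 | ρ = 0.5 | ρ = 0.7 |
|---|---|---|---|
| Interaction significant | 67% | 81% | 95% |
| Given significance, Holm over two between-group tests | 8.0% | 14.0% | 26.4% |
| Same, correct error | 3.5% | 3.4% | 3.7% |
| Given significance, Holm over all four simple effects | 4.8% | 9.4% | 20.2% |
| Same, correct error | 1.9% | 1.8% | 2.1% |

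Multiplying by the first row gives rates over all datasets:
- Holm over two: 0.67 × 8.0 = 5.4%, 0.81 × 14.0 = 11.3%, 0.95 × 26.4 = 25.1%.
- Holm over four: 0.67 × 4.8 = 3.2%, 0.81 × 9.4 = 7.6%, 0.95 × 20.2 = 19.2%.

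In the same scenario, a 95% interval for the hypoglycemia group difference built from the planned error, after a significant interaction, covers 91% / 85% / 73%. With the correct error it covers 95–96%.

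**No true effect anywhere.** The interaction gate holds family-wise error at 2.7% / 3.1% / 3.5% (Holm over four). The ANOVA diagnosis main effect rejects in 4.9–5.1%, so it is unaffected.

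**The case against.** The strongest objection is that the default path may seldom be used. The only group SDs in the documents are 0.066 and 0.020, a variance ratio of 0.004356 / 0.0004 = 10.9. With that ratio and 17 per group, Box's test rejects almost always, so the covariance pattern model would take over, and a model with separate group covariances has no single interaction variance. This lowers the expected impact but does not remove the defect. Those SDs belong to acetate-supplied glial oxidation, not neurotransmitter levels. The fallback is triggered by unequal covariances, not by ρ > 0. The t-test sentence follows it without saying which error then applies. If the interaction term is still used with these unequal SDs, the inflation is essentially unchanged.

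The second objection is reach, and it stands as a limit. The primary endpoint is ketone uptake and metabolism, and the documents do not clearly give tracer measures at both levels: Session C says "Once hypoglycemia is achieved tracer will be administered", although Cohort 2 is described as combining both levels with tracer. Even Cohort 3 is not fully settled, since its schedule lists Session B with a clamp while the Session B text describes none. The 17-per-group reasoning is also not extended by name to the no-tracer cohort.

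Third, the interaction gate protects when nothing differs, and with Holm over four tests at ρ = 0.3 the false-positive rate does not exceed 5%. Both are true. But the tests are meant for the case where an interaction is real, and there the gate gives little protection at ρ of 0.5 or more. The coverage figures illustrate the same error; the statistical text itself specifies tests, not intervals.

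**Conclusion.** The concern holds. As written, the plan gives the unpaired group contrasts a standard error equal to √(1−ρ) times the correct one. The direction follows from the algebra for any ρ > 0; the size depends on a ρ that the documents do not supply. Under the planned gate and Holm, excess over 5% is slight or absent at ρ = 0.3 and clear at 0.5 to 0.7, where false group differences at euglycemia reach 9–14% and 20–26% once the interaction is significant. At ρ = 0 there is no error.

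The finding is confined to follow-up contrasts on outcomes measured at both glycemic levels. It does not affect the paired contrasts, the diagnosis main effect or the sample size. It should be fixed before analysis.

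**What to change.** Amend the follow-up sentence in both Statistical Considerations passages:

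1. Keep the subject-by-condition (interaction) error for paired within-group contrasts.
2. For unpaired group contrasts at each clamp condition, use the between-subject variance at that condition: a Welch two-sample t-test, or contrasts from a mixed model with unstructured, group-specific covariance.
3. State that the same rule applies when the covariance pattern model is used.
4. Keep Holm and name its family: the two between-group tests, or all four simple effects.

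The cost is a sentence or two of wording, with no new data or subjects. Any between-group intervals reported become wider, and some follow-up contrasts that would have been called significant will not be.

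### The stated 80% power is for one unadjusted t-test under hypoglycemia, but the analysis text makes that t-test a Holm-corrected follow-up of a significant interaction

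*Combined protocol and SAP*

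**What the plan says.** Both parts are in Section V, item 6 (Statistical Considerations). They are repeated almost word for word in the second Statistical Considerations item (numbered 12), after the safety monitoring plan.

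- **Sample size.** The planning data come from one condition: "under hypoglycemic conditions, we observed significantly greater fractions of glial oxidative metabolism supplied by acetate in T1DM subjects compared to non-diabetic controls". The calculation is "With a pooled standard deviation of 0.033" and "17 diabetic subjects and 17 non-diabetic controls", which "will provide 80% power at the two-sided 0.05 significance level to detect differences of 0.033". It mentions no repeated measures, interaction or multiplicity. Section V, item 6 carries the same group sizes over to the glucose/lactate and cognitive cohorts.
- **Analysis.** Group comparisons are by repeated-measures ANOVA. A later sentence begins "Evaluation of a significant diagnosis by clamp condition interaction" and assigns that evaluation to paired or unpaired t-tests, "using the interaction variance term from the ANOVA with a Holm correction for multiple testing".

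The plan does not say which test decides the primary endpoint, which contrasts share the Holm family, what within-subject correlation is expected, or what group difference is expected at euglycemia.

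**The concern.** The contrast that was powered, diabetic versus control under hypoglycemia, appears in the analysis text only as one of the t-tests that follow a significant interaction. Two features of that route are absent from the power calculation: the interaction must first be significant, and the t-test is then Holm-adjusted.

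The gate matters most if enhanced fuel use is already present at euglycemia, because the interaction then shrinks or vanishes. The protocol's own background leaves this open. Section 2.1.3 reports faster label appearance at euglycemia in recurrently hypoglycemic animals given lactate, but only a small change in acetate utilization at euglycemia.

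With no deciding test named, a positive result could also be claimed from the main effect, the interaction or a follow-up test after the data are seen.

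**Working it through.** **Inputs from the plan (Section V, item 6):** n = 17 per group, difference 0.033, SD 0.033, two-sided 0.05. The plan's SD is accepted throughout. The standardised difference is d = 0.033/0.033 = 1.0.

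**Assumptions (not in the documents):** correlation ρ between a subject's two conditions of 0.3, 0.5 or 0.7; fraction f of the group difference also present at euglycemia of 0, ½ or 1; Holm over two or four tests (four meaning two between-group and two within-group); equal variances; no dropout.

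**Step 1: the plan's figure.** Two-sample t, df = 32, noncentrality d·√(n/2) = 1.0 × √8.5 = 2.915, critical value 2.037. Power is 80.7%, which reproduces the stated 80% as one unadjusted test.

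**Step 2: Holm alone.** Holm tests its smallest p-value at 0.05/m. With the same noncentrality:

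| Tests m | Level | Power | n per group for 80% |
|---|---|---|---|
| 1 | 0.05 | 80.7% | 17 |
| 2 | 0.025 | 71.2% | 21 |
| 4 | 0.0125 | 60.8% | 24 |

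Holm is step-down, so a contrast ranked second or later faces a milder level. The 71% and 61% are floors for the ungated test.

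**Step 3: the gate and the main effect.** In units of the SD:

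- Interaction: standardised effect (1 − f)/√(2(1 − ρ)). At f = 0 and ρ = 0.5 this is 1/√1 = 1.0, so power is 80.7%.
- ANOVA group effect: standardised effect [(1 + f)/2]/√((1 + ρ)/2). At f = 1 and ρ = 0.7 this is 1/√0.85 = 1.085, so power is 87%.

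The gate-plus-Holm columns come from simulation with four tests, counting trials in which the interaction is significant at 0.05 and the hypoglycemia group contrast then passes Holm. Cells give ρ = 0.3 / 0.5 / 0.7.

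| Group difference at euglycemia | Gate alone | Gate + Holm, ordinary error term | Gate + Holm, interaction variance term | Ungated ANOVA group effect |
|---|---|---|---|---|
| None | 67 / 81 / 95% | 52 / 58 / 64% | 60 / 74 / 90% | 42 / 37 / 34% |
| Half | 22 / 29 / 45% | 20 / 24 / 34% | 22 / 28 / 44% | 75 / 69 / 63% |
| Equal | 5% | 3% | 3–5% | 94 / 90 / 87% |

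**Step 4: the error term.** The interaction mean square estimates σ²(1 − ρ), while a between-group contrast within one condition has error variance σ². Using the former multiplies the standard error by √(1 − ρ) = 0.84, 0.71 or 0.55. A nominal 0.05 test then rejects a true null with probability P(|t₃₂| > 2.037·√(1 − ρ)). The cut-offs are 1.70, 1.44 and 1.12, giving about 10%, 16% and 27%. The higher rejection rates in the fourth column are therefore lost error control, not power.

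**Step 5: can the interaction be estimated?** In the cohort descriptions (Section V, item 4), Cohort 1 has a euglycemic scan without clamp and a hypoglycemic clamp scan with tracer. Session B is without tracer, and Session C starts the tracer after hypoglycemia is reached. A tracer-based endpoint in Cohort 1 has no euglycemic value, so no diagnosis-by-clamp interaction exists for it. Cohort 2 is described as combined eu- and hypoglycemia with tracer, so this limit is specific to Cohort 1.

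**The case against.** A reader might infer that the trial's actual power is well below 80%, or should be restated as 61% or less. The documents do not support either.

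- The ANOVA group comparison is planned without any stated condition. Only the t-tests clearly wait for the interaction. Where the gate does worst (equal difference, 3%), the ungated group effect has 87–94% power. This stands, though that effect has only 34–42% power when the difference exists under hypoglycemia alone, which is the condition the sample size was built on.
- The Holm family, the correlation and the euglycemic difference are not given, and 61% is a floor for ungated Holm over four tests. This stands.
- Under the interaction variance term as written, gated rejection reaches about 90% at correlation 0.7. This is correct arithmetic, but Step 4 shows that it is bought with inflated type I error.
- The plan expects an effect nearer the preliminary one (0.19 versus 0.10, "90% increase in diabetics compared to controls"). At 0.09 with SD 0.033, d = 2.73 and Holm costs almost nothing. Gated power is 90–100% if the euglycemic difference is at most half (correlation 0.3 to 0.7). It is about 5% if the difference is equal, where the group effect is near 100%. This limits the practical loss, but the 80% claim is made at 0.033.

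**Conclusion.** The mismatch holds: the stated 80% is a property of one unadjusted unpaired t-test and not of the interaction-gated, Holm-corrected route by which the plan reaches that contrast. At a difference of 0.033 and the plan's SD, the strictest Holm step alone gives 71% (two tests) or 61% (four). The further effect of the gate cannot be fixed from the documents. Under the assumptions listed and a valid between-subject error term, power for the gated contrast is about 52–64%, 20–34% or 3%, depending on how much of the difference is present at euglycemia.

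Two related faults sit in the same sentence of the plan: a within-subject error term for between-group contrasts, and an interaction that cannot be estimated for tracer endpoints in Cohort 1. The documents do not show that the study as a whole is underpowered, because they never say which test decides the primary endpoint.

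**What to change.** State in both Statistical Considerations items:

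1. The diabetic-versus-control comparison under hypoglycemia is the single primary test, at two-sided 0.05, done whatever the interaction result and with a between-subject error term.
2. The remaining contrasts are listed by name, are secondary, and share the Holm correction.

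This takes a few sentences and no extra subjects. The 80.7% then refers to the test actually used, on the plan's SD, and the test can be run in Cohort 1. The cost is that the other contrasts become secondary. If the difference is equal in both conditions, the primary test also forgoes the somewhat higher power of the ANOVA group effect (87–94%).

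If the gated, Holm-corrected procedure is really intended, recompute and restate its power with the correlation, the euglycemic difference, the Holm family and the error term written down, and say what replaces the interaction where the tracer is given only under hypoglycemia.
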